## **STUDY OUTCOME MEASURES (ENDPOINTS)**

Please refer to [Table 1](#).

## **DATA MANAGEMENT AND QUALITY PLAN**

### **Data De-identification**

Participants will be enrolled using Cerner’s Patient Protocol Manager; the application assigns each participant a unique participant identifier, or “PID”. This PID is a code consisting of a combination of numerals and letters, which serves as the identifier for this participant for this research study and links them back to their hospital medical record and their protected health information (PHI). Access to the “link” between the PIDs, the PHI, and to the clinical data are only granted to the clinical research team as assigned on the Delegation of Authority Log. All the clinical research data is recorded in a de-identified fashion onto our paper source documents, which is then transcribed into our electronic case report forms (eCRFs). The eCRF is used for storage (a database) and facilitates analysis. Clinical data generated by research devices also uses the PID, and once the data has been transformed into interpretable results, it is stored into the Clinical Research Database. Both storage locations are secured and only accessible to the assigned clinical research team. The “link” will only be used to re-identify participants in the event of a serious adverse event (SAE) requiring identification of a PID and PHI to treat the participant. The “link” will be stored in the Patient Protocol Manager and in Clinical Research Database, where only the TRI-MD research team has access. These secure databases are stored/accessed on the AdventHealth Orlando password-protected computer network. No one outside of AdventHealth Orlando investigators or researchers will have access to the databases.

### **Data Confidentiality, Storage, and Retention**

The identity and personal health information will be kept confidential to the extent permitted by the applicable laws and/or regulations and will not be made publicly

available. If results of this study are published or presented, identities will not be revealed. Confidentiality will be maintained during and after the study. This information is also included in the informed consent, which is discussed with each participant prior to enrollment.

All paper sourced study documentation will be stored in the medical records room at TRI-MD, which is behind badge access doors, continuously locked, monitored and provides for limited access. The data records may also be stored as electronic records. This data is safeguarded so that only those on the research team have access to it via limited badge access to the medical records room (paper) or role relationship (electronic). The electronic data is maintained under Adventist Information Technology security controls.

The duration of study data retention will be determined by governing FDA regulations and/or sponsor contract mandate (if applicable). TRI-MD retention policy is maintained in the Records Management Policy. Electronic de-identified data will be kept indefinitely in our data warehouse.

## **Data Quality**

Data quality and integrity will be governed by the system of ISO 9001 driven data management SOPs. These SOPs delineate how quality is built into the identification, collection, handling, and processing of the data.

The types of data collected may include data that are: (a) manually abstracted or electronically extracted from medical records, (b) observed in clinical exams, (c) obtained from laboratory and diagnostic tests, or from various biological monitoring or imaging devices, and (d) patient-reported items. Each data type can be understood by its source and the associated collection mechanism. Only the SOPs/SSPs and associated workflows applicable to the study will be used.

Within the study, quality control steps may include:

- Source Data Verification (SDV)
- Query Management
- Parallel Processing by a second party
- Complete re-processing of a percentage of the data and comparing to the original
- Change Control (if changes are made there will be documentation that covers change content, rationale, author, time and date)

## **Data Sharing (Outside of AdventHealth Orlando)**

This is a AdventHealth-Orlando sponsored clinical study with Pfizer as the funder. De-identified results from this study will be shared with collaborators at Pfizer to conclude analysis and prepare data for publication. However, only AdventHealth Orlando will have access to the clinical data and the code to identify the samples and make the link between lab and clinical data. The source documentation will remain at TRI-MD.

Some of the endpoint testing and post-acquisition data analysis will be conducted at outside laboratories/institutions including, but not limited to, OWL Metabolomics, HepQuant, Nordic Bioscience, Jackson Laboratories, Perspectum Diagnostics

and AMRA. To perform these analyses/testing/etc. and to interpret results, certain data elements may need to be shared along with the biospecimen samples. The governance of data sharing is detailed in the Contract with the Funder and in associated Vendor Agreements. When these documents are not available, Data Use Agreements (DUAs) or Lab Services Agreements, as appropriate, will be obtained, which will identify the specific data elements to be shared (if any) and will govern the sharing of data related to this study. Data will be de-identified, but a link/code is managed within an electronic research management system and maintained by a study coordinator.

Should archived biospecimens be needed for research outside of AdventHealth Orlando that is beyond the details in the Contract with the Funder and in associated Vendor Agreements and certain data elements that are connected to the archived biospecimen samples are needed to conduct the research, then DUAs will be obtained. The DUAs will identify the purpose for data sharing, the specific data elements to be shared, and will govern the sharing of data related to this study. Data will be de-identified, however a link/code is managed within an electronic research management system and maintained by a study coordinator.

## **SAMPLE SIZE DETERMINATION**

Sample size calculations are based on the two primary endpoints, percent change in PDFF and MRE. Based on a literature review it is assumed that the mean percent change from baseline in PDFF at 12–16 weeks has a standard deviation of 30%, the mean change from baseline in MRE has a standard deviation of 1 kPa. There is no formal hypothesis testing, however, the investigators would like to be able to detect a 30% change from baseline in PDFF and a 0.45 kPa change from baseline in MRE. Using a 1-sided t-test with an alpha level of 0.1, there is greater than 99% power for the PDFF change and greater than 80% power for MRE. Investigators are also interested in detecting a positive correlation between the 2 measures. A test for a correlation greater than zero, with 25 subjects, has greater than 80% power to detect a correlation of 0.42 or greater.

## **STATISTICAL ANALYSIS PLAN**

The following subsection outlines the statistical methods that will be used in the analysis of the study data. Detailed descriptions will be included in the statistical analysis plan (SAP). Any deviations from the SAP will be described in the Clinical Study Report (CSR).

### **Summary Analyses**

The number of subjects enrolled, completed, and discontinued from the study will be summarized. For subjects who did not complete the study, the reasons for withdrawal from the study will be presented.

Demographic and baseline characteristics will be summarized for all enrolled subjects. Continuous variables will be summarized using mean, median, minimum, maximum, quartiles, and standard deviation. Categorical variables will be summarized using relative frequency. Key demographic and baseline variables will be summarized and include, but are not limited to: age, gender, race, ethnicity, height, weight, BMI, etc.

## **Analysis of PDFF and MRE**

Mixed model repeated measures analysis using all measured data will be used to explore changes over time, systematic differences, correlations with other endpoints, and time trends. The models will include baseline values of the measurements and other baseline demographic information as deemed necessary. Figures and tables will be presented. Details of the model and correlation structure will be detailed in the SAP.

Linear mixed models will be used at each time point to calculate the intra-class correlation coefficient between MRE and PDFF. The models will include baseline values of the measurements and other baseline demographic information as deemed necessary. The models will allow for different variance estimates for each test. Correlations, least squares means, and differences in least squares means, along with their corresponding confidence intervals and standard errors, will be presented in tabular form.

Imaging endpoints measured by other technologies as well as non-imaging endpoints will also be examined. Results will be tabulated and graphed as appropriate. Continuous variables will be summarized using mean, median, minimum, maximum, quartiles, and standard deviation. Categorical variables will be summarized using relative frequency. Mixed model repeated measures analyses using all measured data will be used to explore changes over time, systematic differences, correlations with other endpoints, and time trends. The models will include baseline values of the measurements and other baseline demographic information as deemed necessary. Intra-class correlations between endpoints may also be calculated. Details of the model and correlation structure will be detailed in the SAP.

Other exploratory and ad hoc analysis (if done) will be detailed in the CSR and/or SAP.

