## STUDY DESIGN

### Research Design

This is a non-randomized, single-site, biomarker methodology study in subjects with presumed NAFLD and NASH undergoing bariatric surgery. Participants will undergo bariatric surgery along with all pre- and post-surgery medical visits and standard of care laboratory assessments.

Over the course of this study, longitudinal assessments of subjects with NASH or non-NASH NAFLD will be performed using a battery of non-invasive circulating, functional, imaging, and microbiome-based assays to evaluate physiologic changes that occur in response to bariatric surgery.

The specific imaging to be employed in this study includes FibroScan® and MRI to noninvasively evaluate the effects of bariatric surgery on the liver and on extra-hepatic depots of adipose tissue. The FibroScan® instrument applies a technique referred to as vibration-controlled transient elastography (VCTET™) to simultaneously derive measures of stiffness for the assessment of liver fibrosis, and of ultrasound wave attenuation for the assessment of liver steatosis (a measure referred to as the controlled attenuation parameter [CAP™]). Magnetic resonance (MR) assessments will apply scanning methods to interrogate steatosis, inflammation, and fibrosis of the liver through measures derived from proton density fat fraction (MRI-PDFF), proton spectroscopy (MRS-IHL), T1 relaxometry using the LiverMultiScan (LMS) protocol, and MR elastography (MRE), respectively. To assess effects of surgical intervention outside the liver, MRI evaluation of extra-hepatic adipose tissue volumes within visceral and subcutaneous regions, and skeletal muscle will be quantified.

This study will also collect blood samples to investigate the effect of bariatric surgery on longitudinal profiles of several categories of circulating biomarkers and evaluate their utility in tracking NASH disease regression.

Recent advances in metabolomic testing methodologies and associated analysis algorithms have led OWL Metabolomics to define lipidomic signatures for different NAFLD subtypes, and for differentiating NASH from simple steatosis (Barr 2012). Analysis of serum lipid metabolites by two separate logistic regression algorithms was conducted in a recent study of biopsy-proven NAFLD patients. Findings from that study demonstrated that the OWLiver Care analysis is able to discriminate between NAFLD

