## **Study Site(s)/Location(s) and Number of Subjects**

AdventHealth Orlando site locations (campus, physician offices, etc.):

- Celebration Health
- Translational Research Institute for Metabolism and Diabetes

Estimated number of participants: 35

The study will enroll 25 participants with NASH for the full study and 10 participants with non-NASH [NAFLD or normal] to serve as controls. The 10 non-NASH participants will have baseline measurements and perioperative biopsies only. In the unlikely instance that biopsy results do not confirm NASH. Those participants who do not have NASH diagnosis will not continue in the post-surgery study visits and may become part of the 10 participants non-NASH group (see Figure 1 below). Additional participants may be recruited if the analysis of the primary end point (12 weeks) reveals larger variability than anticipated.

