## **Missing Data**

Descriptive summary statistics will use all available data. Repeated measures analyses will also use all available data and are expected to provide unbiased estimates under the assumption that data are missing at random (MAR) under the assumed model.

Examination of informative missing data and sensitivity analyses may be performed if necessary and reported in the CSR. Multiple imputation (MI) may be used for sensitivity or secondary analyses.

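### With one group followed after surgery, baseline-covariate models give intervals for mean change that are too narrow whenever change correlates with baseline

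*Combined protocol and SAP*

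**What the plan says.** Study Site(s)/Location(s) and Number of Subjects states: "The study will enroll 25 participants with NASH for the full study". Of the controls it says: "The 10 non-NASH participants will have baseline measurements and perioperative biopsies only". Table 1 defines both co-primary endpoints as percent change from baseline at 12 weeks, in MRI-PDFF and in MRE.

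Analysis of PDFF and MRE proposes repeated-measures mixed models and, separately, linear mixed models at each time point for the intra-class correlation between MRE and PDFF. Three times it says of the models: "The models will include baseline values of the measurements and other baseline demographic information as deemed necessary". The paragraph on the per-time-point models ends: "Correlations, least squares means, and differences in least squares means, along with their corresponding confidence intervals and standard errors, will be presented in tabular form". The response variable, the baseline value at which least squares means are evaluated and the standard error method are not stated. Details of the model and correlation structure are left to a separate SAP.

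Sample Size Determination plans on a simple test of change: "Using a 1-sided t-test with an alpha level of 0.1". Multiplicity rules out formal testing and treats p-values as descriptive.

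**The concern.** In a randomised two-arm comparison, adjusting for baseline sharpens the treatment contrast, because the baseline mean is common to both arms and drops out. Here no second arm has post-surgery data. With complete data, the least squares mean of change at the average baseline equals the raw mean change, so the covariate adds no information about that mean. It does remove from the residual the part of the change explained by baseline, and the default standard error uses only that residual. The interval is then valid for participants whose mean baseline is exactly the one observed, not for the population from which these 25 are drawn.

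Because the study does no formal testing, its estimates and intervals are its main inferential output. A default implementation of the stated direction could overstate the precision of the 12-week results. The plan also does not say that this interval would differ from the one implied by its planning test.

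**Working it through.** **Inputs.** From the documents: n = 25 followed; SD of percent change in PDFF 30%; SD of change in MRE 1 kPa; effects 30% and 0.45 kPa; one-sided alpha 0.1. Not in the documents: r, the correlation of change with baseline. It is taken over a range.

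**The plan's own figures.** For a one-sample t-test the noncentrality is effect/SD × sqrt(25).
- PDFF: 30/30 × 5 = 5, power 99.99% (stated: above 99%).
- MRE: 0.45/1 × 5 = 2.25, power 82.4% (stated: above 80%).

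Both reproduce. They rest on an unadjusted test, whose standard error includes baseline variation.

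**Standard error.** Write change as D = a + bB + e, where B is baseline.
- Default model variance of the least squares mean at the observed mean baseline: Var(e)/n.
- Variance of the mean change over repeated samples: b²Var(B)/n + Var(e)/n = Var(D)/n.
- Ratio of standard errors: sqrt(Var(e)/Var(D)) = sqrt(1 - r²).

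**Size at n = 25, SD of change 1 kPa (simulated).**

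| \|r\| | SE ratio | Mean 95% half-width, covariate model (kPa) | Paired half-width (kPa) | Coverage, covariate model | Widening if corrected, 1/ratio - 1 |
|---|---|---|---|---|---|
| 0 | 1.00 | 0.409 | 0.409 | 95.0% | 0% |
| 0.3 | 0.95 | 0.390 | 0.409 | 94.0% | 5% |
| 0.5 | 0.87 | 0.354 | 0.409 | 91.4% | 15% |
| 0.7 | 0.71 | 0.292 | 0.409 | 84.8% | 40% |

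The paired interval covers about 95% throughout. On the PDFF scale the paired half-width is 30 × 0.409 = 12.3 points, against 30 × 0.354 = 10.6 at |r| = 0.5.

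A four-visit mixed model with a baseline covariate (pre-post correlation 0.5, so r = -0.5; 400 runs) gave a mean standard error of 0.172 against 0.196 for the paired one. Coverage was 92.0% against 95.8%. The repeated-measures form does not remove the effect.

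**Plausible r for percent change, the actual endpoint.** These inputs are assumptions.
- MRE: lognormal values, mean 3.5 to 4 kPa, SD 0.8 to 1.2 kPa, pre-post correlation 0.3 to 0.7. Then r runs from -0.37 to -0.56. Coverage is about 90 to 93%, against 94 to 95% for the paired interval.
- PDFF: percent change with mean -30 and SD 30, on a right-skewed baseline. Coverage was 95.0% when change was unrelated to baseline, and 94.7%, 94.3% and 91.8% when its correlation with log baseline was 0.2, 0.3 and 0.5 in size. A proportional fall in fat that depends little on the starting value puts PDFF at the mild end.

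**The case against.** The strongest reply is that the plan has not fixed this model. The response, the evaluation point and the standard error are all deferred, and including baseline values does not strictly rule out baseline as one of the responses. The sentence promising least squares means also belongs to the intra-class correlation paragraph, while the repeated-measures paragraph promises only figures and tables. This stands as a limit: the narrowing follows from the natural reading and default software, not from an explicit instruction. It does not remove the point, because listing baseline beside demographics suggests a covariate, and that is the only direction an analyst is given.

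A reader might also infer more than the documents support:
- **That the intervals must be too narrow.** At r = 0 they are not, and at |r| = 0.3 about one point of coverage is lost.
- **That coverage is near 86%, from an absolute-change calculation.** The planning statement that "the mean change from baseline in MRE has a standard deviation of 1 kPa" can be combined with assumed baseline and follow-up spreads to give a large r. Those spreads are not in the documents, and the endpoint is percent change.
- **That every added demographic covariate shrinks the interval further.** One unrelated to change does not. At r = -0.5, going from one to six covariates, the extra ones uninformative, left the mean standard error at 0.171 and widened the half-width from 0.354 to 0.359.
- **That the covariate model contradicts the Missing Data section** ("Repeated measures analyses will also use all available data and are expected to provide unbiased estimates"), because participants without a baseline scan drop out. Their percent change is undefined in any model, and that section already allows multiple imputation for sensitivity or secondary analyses.
- **That the power statements fail.** They do not depend on this model.

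**Conclusion.** The concern holds in a conditional form. If baseline enters as a covariate and software defaults are used, the 12-week interval for mean change is too narrow by the factor sqrt(1 - r²): not at all at r = 0, about 13% at |r| = 0.5 and about 29% at 0.7. For percent change in MRE, coverage of about 90 to 93% is a reasonable expectation, but only under the assumed lognormal inputs. The loss from this cause is likely to be smaller for PDFF. With a common baseline slope across visits, differences between post-surgery visits are largely unaffected.

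Severity is moderate. The study is exploratory with no formal tests, so a reading of this as a must-fix error, or as an inflated type I error, goes beyond what the documents support. It still merits correction before analysis, because the intervals will be read as the precision of the result.

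**What to change.** State in the SAP the response variable and whether baseline is a covariate or a response. For the co-primary and over-time estimates, use one of these:

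1. **Unadjusted mean percent change with its paired t-interval.** This estimates the Table 1 endpoint and has the form of the planning test (for MRE that section planned in kPa, so only the form carries over).
2. **A repeated-measures model with baseline as a response level**, on log values, with Baseline Visit 2 (the last pre-surgery scan) and Visits 4 to 7 as outcomes. Back-transform the Visit 5 minus Baseline Visit 2 contrast to a percent change. A contrast on raw values would give absolute change and would not match Table 1.
3. **If a baseline-covariate model is kept for these estimates**, add slope² × Var(baseline)/n to the squared standard error. This restores coverage to about 95%.

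Otherwise, keep baseline-adjusted models for exploring who responds.

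The cost is SAP wording, with no new data. Intervals widen by about 5%, 15% and 40% at |r| = 0.3, 0.5 and 0.7. Option 2 reports a geometric rather than an arithmetic mean percent change, and the tables should say so.

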## **Multiplicity**

Since this is an exploratory study intended to characterize PDFF and MRE measurements in a bariatric surgery population, no formal hypothesis testing is planned, therefore no multiplicity adjustments will be performed. P-values will be treated as descriptive statistics.

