To evaluate the effect of bariatric surgery on extrahepatic adipose depots, skeletal muscle, and liver fibro-inflammatory state in adults with NASH over time	
Percent change from baseline, over time post-surgery (42 days [6 weeks], 84 days [12 weeks], 182 days [26 weeks], and 364 days [52 weeks]), in:
 
 
• extrahepatic volumes of adipose tissue and skeletal muscle as assessed by MRI body composition profiling
 
• corrected-T1 of the liver as assessed by LiverMultiScan MRI
 

To evaluate the effect of bariatric surgery on kinetic measures of liver function in adults with NASH over time	
Percent change from baseline, over time post-surgery (42 days [6 weeks], 84 days [12 weeks], 182 days [26 weeks], and 364 days [52 weeks]), in Disease Severity Index (DSI) and %-shunt as assessed by HepQuant SHUNT

To evaluate the effect of bariatric surgery on gut microbiome in adults with NASH over time	
Change from baseline, over time post-surgery (42 days [6 weeks], 84 days [12 weeks], 182 days [26 weeks], and 364 days [52 weeks]), in stool sample:
 
 
• composition (shotgun analysis of microbiome DNA)
 
• functionality (shotgun analysis of microbiome RNA)
 
• metabolites of microbiota
 

To evaluate the effect of bariatric surgery on circulating metabolomics, protein biomarkers, and liver enzymes in adults with NASH over time	
Percent change from baseline, over time post-surgery (42 days [6 weeks], 84 days [12 weeks], 182 days [26 weeks], and 364 days [52 weeks]), in:
 
 
• OWLiver, and OWLiver Care metabolomics panels from OWL
 
• pro-collagen protein fragments panel from Nordic Bioscience
 
• aspartate aminotransferase (AST) and alanine aminotransferase (ALT) enzymes
 

To evaluate pre-surgery differences in biomarker signatures between adults with NASH and those with non-NASH NAFLD	
Difference measures between subject groups at baseline for:
 
 
• FibroScan®-derived CAP™ and stiffness
 
• magnetic resonance (MR)-derived measures
 
• circulating biomarker measures
 
• gut microbiome measures
 

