## Circulating Biomarkers

Assessment of circulating biomarkers will be performed at scheduled visits as outlined in [Appendix A: Schedule of Events](#).

**Metabolomics:** A comprehensive panel of serum metabolites will be measured at OWL Metabolomics. This panel of biomarkers allows for the identification and monitoring of disease progression / regression based on changes in the metabolomic signature of highly specific circulating lipid components. The panel includes OWLiver®, OWLiver®Care, and approximately 600 additional metabolites for exploratory purposes. This testing paradigm will allow for a comprehensive evaluation of changes in liver health and metabolic status after bariatric surgery/

**Hepatic Panel:** This panel includes total protein, albumin, globulin, albumin/globulin ratio, total bilirubin, direct bilirubin, alkaline phosphatase, alanine aminotransferase (ALT), and aspartate aminotransferase (AST). It is a standard clinical test commonly used to determine the health of the liver.

**Pro-Collagen Protein Fragments:** At minimum, we will measure two pro-collagen protein fragments at Nordic Bioscience- ProC3 and ProC6. Nordic Bioscience has developed a panel of biomarkers of extracellular matrix turnover that could provide important information about liver health including inflammation, disease prognosis, efficacy of interventions, and fibrogenesis.

We will bank additional samples for future assessment of novel biomarkers and mechanisms.

Details regarding type of sample, matrix, tubes, volume and sample management conditions for collection will be described in the Laboratory Manual.

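### The rule against multiplicity adjustment is justified only for PDFF and MRE, but it also covers about 600 metabolites and the shotgun microbiome features, so the false share of any selected list would be unknown

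*Combined protocol and SAP*

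**What the plan says.** The Multiplicity section describes an "exploratory study intended to characterize PDFF and MRE measurements in a bariatric surgery population", concludes that "no multiplicity adjustments will be performed", and adds that "P-values will be treated as descriptive statistics". It names no endpoint to which the rule does not apply.

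The measurements go well beyond PDFF and MRE:

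- Circulating Biomarkers adds "approximately 600 additional metabolites for exploratory purposes" to the two named lipidomic tests. Under Study Visits, the panel is drawn at both baseline visits and at all four post-surgery visits.
- Table 1 has exploratory endpoints for stool microbiome composition (DNA), function (RNA) and metabolites at four post-surgery visits. It also has a baseline comparison of NASH with non-NASH participants on circulating and microbiome measures, and correlations of histology with the other secondary and exploratory endpoints.
- Analysis of PDFF and MRE says "Imaging endpoints measured by other technologies as well as non-imaging endpoints will also be examined", using the same kind of repeated-measures mixed model as for PDFF and MRE.

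On numbers, "The study will enroll 25 participants with NASH for the full study", and 10 non-NASH participants contribute baseline data and biopsies only. The documents give no false-discovery control, feature filter, selection threshold or validation step for the large panels.

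**The concern.** Not adjusting is reasonable for two co-primary imaging measures that are reported descriptively. A screen of hundreds of features is different, because someone has to decide which features to carry forward. The plan has such aims: Research Design wants to know whether circulating markers can track regression of NASH and whether the microbiome offers non-invasive markers, and Table 1 wants to know how well the biomarkers characterise disease state.

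The only per-feature measure of evidence that the Multiplicity section mentions is the unadjusted p-value. Calling it descriptive does not tell a reader how many features on a list are there by chance. At stake is effort spent following up markers that do not replicate.

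**Working it through.** **The plan's own figures.** The documents give no false-positive or false-discovery figure. The only error rate is the one-sided 0.10 in Sample Size Determination, used for power. With n = 25 and the noncentral t distribution, the PDFF target (30%/30% = 1.0 SD) has 99.99% power and the MRE target (0.45/1 = 0.45 SD) has 82.4%. A correlation of 0.42 has 81.1% by simulation of the exact test (79.3% by the Fisher z approximation). The stated powers of over 99%, over 80% and over 80% therefore reproduce, apart from the slightly lower approximation for the correlation.

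**Inputs.** From the documents: m = 600 metabolites; 25 NASH participants followed over time; 25 versus 10 at baseline (taking the circulating measures in that comparison to include the 600). Assumed: selection at two-sided p<0.05; the share π of features that truly differ; and the standardised effect d. The value d = 0.45 is the plan's own MRE target in SD units; the others are illustrative.

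**Chance findings per contrast.** If all 600 are truly null, m × α = 600 × 0.05 = 30. This expectation does not require independence.

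**False share of a selected list.** Expected false share = α(1−π) / [α(1−π) + π × power].

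Worked case, 25 versus 10, d = 0.8, power 0.546, π = 5%: (0.05 × 0.95) / (0.05 × 0.95 + 0.05 × 0.546) = 0.0475 / 0.0748 = 0.635.

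| Contrast | d | Power | π = 5% | π = 10% | π = 30% | π = 50% |
|---|---|---|---|---|---|---|
| 25 vs 10, baseline | 0.5 | 0.254 | 79% | 64% | 31% | 16% |
| 25 vs 10, baseline | 0.8 | 0.546 | 64% | 45% | 18% | 8% |
| Within-patient, n = 25 | 0.45 | 0.579 | 62% | 44% | 17% | 8% |
| Within-patient, n = 25 | 0.8 | 0.970 | 50% | 32% | 11% | 5% |

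**When would most of the list be false?** The share exceeds one half when π < α/(α + power). At power 0.254 this is 0.05/0.304 = 16%. At power 0.998 (within-patient, d = 1.0) it is 0.05/1.048 = 5%. The break-even is thus about 5–16% over d = 0.3 to 1.0 within patients and d = 0.5 to 1.0 between groups.

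**What q-values would do.** Simulation with 600 independent features, 400 runs per case, selecting at q<0.10:

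| Contrast, d, π | Unadjusted: true / false picks | q<0.10: true / false picks | Mean false share, before → after |
|---|---|---|---|
| Within-patient, 0.8, 5% | 29.1 / 28.8 | 23.8 / 2.8 | 49% → 10% |
| Within-patient, 0.45, 5% | 17.4 / 28.5 | 2.1 / 0.4 | 62% → 9% |
| 25 vs 10, 0.8, 5% | 16.3 / 28.7 | 1.9 / 0.4 | 64% → 8% |
| 25 vs 10, 0.8, 30% | 97.9 / 20.7 | 51.0 / 4.0 | 17% → 7% |

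The mean false share counts a run with an empty list as zero, so for short lists it is lower than the ratio of the two averages.

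**Not quantified.** The number of microbiome features is not given. As an illustration, 1,000 to 5,000 null features would give 50 to 250 picks at p<0.05.

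**The case against.** The case on the other side has real force.

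- The study calls itself exploratory, plans no formal tests and treats p-values as descriptive. No stated error rate is breached, and the documents do not say that features will be chosen by p-value. This stands, and it is why 0.05 is an assumption here.
- The 600 metabolites are already called exploratory, and detail is deferred to a separate SAP and the study report. That SAP is not among the documents and could add control. It would, however, start from a rule that says the opposite without exception.
- q-values shorten lists. At q<0.10 the baseline contrast with d = 0.8 and 5% true features yields about 2 true picks instead of 16. This stands as a cost, though it also shows how little that contrast can support.

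A reader might go further and infer any of the following. The documents do not support them.

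- *Most selected features will be false.* This holds only if the share that truly differs is below about 5–16%, which the documents do not give. It is least plausible for change after surgery: the Background chose this population because surgery is known to affect NASH, so many metabolites may truly change.
- *The four visits produce 120 false hits (30 × 4).* That needs a separate test at each visit and no true change. The plan describes repeated-measures models over time, and the hits would share patients and a baseline.
- *The plan screens at 0.10.* That level is one-sided and appears only in the sample-size calculation.
- *All of this rests on 25 people.* That fits the longitudinal analyses. The baseline comparison is 25 versus 10, and the histology correlations use the entire population, planned at 35.

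**Conclusion.** The gap is real but modest. A rule argued from two imaging measures is applied, without exception, to panels for which it was not argued, and nothing in these documents would tell a reader what share of a selected list is likely to be false.

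If p<0.05 were used to select, about 30 of 600 null metabolites would be picked per contrast. The false share would be about 64–79% (25 versus 10) or 50–62% (within-patient) if 5% of features truly differ, and about 5–31% at the 30% and 50% shares examined. These figures rest on the assumed threshold, shares and effect sizes; the simulation also assumes independent features. The imaging endpoints are unaffected. This is an inexpensive reporting improvement, not a flaw that invalidates the study.

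**What to change.** In the Multiplicity section, limit the unadjusted rule to the co-primary and secondary imaging endpoints. Then add that, for each high-dimensional family (serum metabolites, microbial taxa, microbial functions, stool metabolites):

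1. Benjamini-Hochberg q-values are reported beside raw p-values, with the family and the contrast defined in advance.
2. Any highlighting uses a q threshold stated in advance, for example 0.10.
3. Results are labelled hypothesis-generating.

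A q-value is itself descriptive, so this fits the study's exploratory stance and introduces no formal test. The cost is a short SAP addition and a routine computation, with no extra data, visits or participants. The downside is that few features may be highlighted, particularly in the 25 versus 10 comparison. The 0.10 is a convention and can be set differently, provided it is fixed before the data are seen.
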